- ² All patients who are on a stable background LMT will enter a 2-week screening period except for those from a previous evinacumab study who completed an end of study visit within 7 days prior to the baseline/day 1 visit for this open-label study.
- ³. Patients who completed an end of study visit in a previous evinacumab study within 7 days of the baseline/day 1 visit for this open-label study do not have to undergo the screening visit and may enroll directly into this study. The EOS visit from the previous study can serve as the baseline/day 1 visit for this open-label study and overlapping assessments do not need to be repeated in this study. Only those assessments and procedures not done in the previous study must be conducted at the baseline visit. These specific assessments to be administered to all patients are identified in the Schedule of Events, [Table 3](#).
- ⁴. Starting on day 1 (baseline), patients will receive evinacumab 15 mg/kg IV administered Q4W.
- ⁵. Patients will be followed for 24 weeks after receiving the last dose of study drug. Patients who enter a CUP, EAP, or ISS/IST may forgo the 24-week follow-up period after the last dose. For these patients, the EOT visit will be their last visit.

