12. PK sample collected in all patients. For patients undergoing apheresis, a PK sample should be collected immediately before the apheresis procedure. For patients undergoing plasma exchange, a PK sample should be collected immediately before and after the procedure. For patients who are not undergoing apheresis, the PK sample should be drawn before the dose of study drug.
13. After the week 24 visit, visits are in a strict sequence of A through F and should occur every 4 weeks. After visit F, the sequence repeats (visits A through F) until the end of treatment visit.
14. The end of treatment visit should occur 4 weeks post the last dose. Patients who prematurely discontinue from study drug should return to the clinic within 5 days if possible for end of treatment visit assessments. At this visit, WOCBP will be provided with urine pregnancy tests with instructions to test for pregnancy at home every 4 weeks after this visit and Q4W when phone visits are scheduled (weeks 8 and 16 post last dose). Urine pregnancy testing will be done during clinic visits at week 12, week 20, and week 24. Patients who upon their study completion, may continue to receive treatment outside of the clinical trial (such as through a CUP, EAP, or ISS/IST) and thereby may forgo the 24-week follow-up period of the study. The follow-up period was intended to be an off-drug follow-up. No off-drug follow-up period is required for these patients. In this situation, the patient's EOT will be their last study visit.

15. At weeks 8 and 16 of the follow-up period all patients will be contacted by phone to query LMT compliance, to inquire about AEs or changes to concomitant medications, confirm required contraception use, and remind patients of pregnancy reporting. Women of childbearing potential will report the results of their home pregnancy test. Patients who upon their study completion, may continue to receive treatment outside of the clinical trial (such as through a CUP, EAP, or ISS/IST) and thereby may forgo the 24-week follow-up period of the study. No off-drug follow-up period is required for these patients. In this situation, the patient's EOT will be their last study visit.
16. Should be collected at the baseline visit or at any study visit for patients who have not previously been enrolled in an evinacumab or alirocumab clinical study.
17. PK sample (including ANGPTL3) only for evinacumab-naïve adolescent patients.

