9.4.6. Follow-up

Adverse event information will be collected until the patient's last study visit.

Serious adverse event information will be collected until the event is considered chronic and/or stable.

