2.3. Study Plan

This study consists of 4 periods: a run-in period (for patients who may require HoFH genotyping, patients whose background medical LMT has not been stable prior to screening, or those whose apheresis settings and/or schedule have not been stable for at least 8 weeks prior to screening), a 2-week screening period, an open-label treatment period, and a 24-week follow-up period after the last dose of study drug (See [Figure 1](#) below)

Study duration will vary for each patient in this open-label study designed to evaluate the long-term safety and efficacy of evinacumab in patients with HoFH. It will range from months up to approximately 4 years, depending on conditions met in protocol Section 5.1, including IP regulatory approval.

Figure 1: Study Flow Diagram

- ¹. Patients who may require HoFH genotyping and patients whose background LMT/apheresis settings and/or schedule has not been stable prior to baseline (day 1) will enter an up to 10-week run-in period.
- ² All patients who are on a stable background LMT will enter a 2-week screening period except for those from a previous evinacumab study who completed an end of study visit within 7 days prior to the baseline/day 1 visit for this open-label study.
- ³. Patients who completed an end of study visit in a previous evinacumab study within 7 days of the baseline/day 1 visit for this open-label study do not have to undergo the screening visit and may enroll directly into this study. The EOS visit from the previous study can serve as the baseline/day 1 visit for this open-label study and overlapping assessments do not need to be repeated in this study. Only those assessments and procedures not done in the previous study must be conducted at the baseline visit. These specific assessments to be administered to all patients are identified in the Schedule of Events. The Study event table is presented in Appendix 10.5 in protocol.
- ⁴. Starting on day 1 (baseline), patients will receive evinacumab 15 mg/kg IV administered Q4W.
- ⁵. Patients will be followed for 24 weeks after receiving the last dose of study drug.

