4.8.1. Adverse Events Variables

The period of safety observation starts from the time when the patient gives informed consent and continues into the following periods:

- The PRE-TREATMENT period is defined from the day the ICF is signed to the day before the first dose of open-label study treatment administration.
- The open-label treatment-emergent adverse event (TEAE) period is defined from the day of the first open-label study treatment administration to the day of the last open-label study treatment administration + 168 days (24 weeks).
- The POST-TREATMENT period is defined from the day after the end of the TEAE period to the last study visit.

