5. STATISTICAL METHODS

In general, data will be summarized and presented in three patient groups, depending on the status of previous evinacumab treatment exposure:

- Continue Evinacumab: Patients who received evinacumab in a previous study (eg, R1500-CL-1331 or R1500-CL-1629);
- New Evinacumab: Patients without previous exposure to evinacumab (ie, evinacumab naïve);
- Total: All patients, regardless of previous (or not) evinacumab exposure.

These 3 evinacumab exposure groups will be provided for all patients in the respective patient analysis sets. Assuming there are enough adolescent patients (age ranging from 12 years to < 18 years old) to perform an evaluation, the three evinacumab treatment exposure groups will be provided again for the subpopulation of adolescent patients [yes/no]. The subpopulation of adolescent patients has two categories, specifically the patient is an adolescent defined as ranging in age from 12 years to < 18 years old, or the patient is not an adolescent (i.e. an adult) defined as ≥ 18 years of age. Unless otherwise noted, data from both adolescent and adult patient subgroups will be summarized.

Continuous data will be summarized descriptively using the number of patients with data, mean, SD, median, minimum and maximum for each patient group for the study. First quartile (Q1) and third quartile (Q3) will be also provided for baseline lipid parameters, HbA1c, and hs-CRP.

Categorical and ordinal data will be summarized using the number and percentage of patients for each patient group for the study.

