5.8.1. Adverse Events

In general, the primary focus of AE reporting will be on TEAEs summarized in TEAE period. Post-treatment AEs will be summarized separately.

If an AE onset date (occurrence, worsening, or becoming serious) is incomplete, an imputation algorithm will be used to classify the AE as pre-treatment, treatment-emergent, or post-treatment. The algorithm for imputing date of onset will be conservative and will classify an AE as treatment-emergent unless there is definitive information to determine pre-treatment or post-treatment status. Details on classification of AEs with missing or partial onset dates are provided in Section 6.3.

Adverse event incidence tables will present the number (n) and percentage (%) of patients experiencing an AE by SOC and PT. In addition, incidence tables by SOC, HLG, HLT, and PT will be provided for all TEAEs, serious TEAEs, and TEAEs leading to permanent treatment discontinuation. Multiple occurrences of the same event in the same patient will be counted only once in the tables within a treatment phase (TEAE or post-treatment AE). For tables presenting by severity of events, the worst severity will be chosen for patients with multiple instances of the same event. The denominator for computation of percentages is the safety analysis set within each patient group, and again for the subpopulation of adolescent patients.

AE incidence tables will present data by SOC sorted alphabetically and PT sorted by decreasing frequency of the overall patient, and summarize the number (n) and percentage (%) of patients experiencing an AE.

The event rate per patient-year (the number of patients with an event divided by total patient-years) will be provided in the table for all TEAEs by SOC and PT. For a patient with an event, patient-year is censored at time of first event. For a patient without an event, patient-year corresponds to the length of the TEAE period.

Analysis of all treatment-emergent adverse events

The following TEAE summaries will be generated:

- Overview of TEAEs, summarizing number (%) of patients with any
 - TEAE;
 - Serious TEAE;
 - TEAE leading to death;
 - TEAE leading to permanent treatment discontinuation.
- All TEAEs by primary SOC, HLG, HLT, and PT
- All TEAEs by primary SOC and PT
- Number (%) of patients experiencing common TEAE(s) presented by primary SOC and PT (PT incidence $\geq 5\%$ in any patient group)
- All TEAEs relationship (related/not related) to evinacumab

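### The TEAE rate credits event-free patients with time to last dose + 168 days, but patients who move to treatment outside the trial may stop about 28 days after the last dose; the same rate is absent from the serious-event tables

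*SAP*

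**What the plan says.** **Rate.** SAP 5.8.1 defines a rate per patient-year: patients with an event divided by total patient-years. It "will be provided in the table for all TEAEs by SOC and PT", and no other table is named. Time stops at the first event for patients who have one. "For a patient without an event, patient-year corresponds to the length of the TEAE period". SAP 4.8.1 runs that period from the first open-label dose "to the day of the last open-label study treatment administration + 168 days (24 weeks"). Protocol 10.4.4.1 uses the same end point. Neither document cuts the period at the last visit.

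**Follow-up.** Protocol Figure 1, footnote 5 states: "Patients who enter a CUP, EAP, or ISS/IST may forgo the 24-week follow-up period after the last dose". The EOT visit is then the last visit. Table 3, footnote 14 fixes its timing: "The end of treatment visit should occur 4 weeks post the last dose". Protocol 9.4.6 reads "Adverse event information will be collected until the" patient's last study visit. SAP Figure 1 still has all patients followed for 24 weeks, and the SAP schedules for amendments 5A and 5B contain no such waiver.

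**Other safety outputs.** Percentages use the safety analysis set (SAF) within each group. Serious TEAEs get incidence tables and listings. Positively adjudicated CV events get a number of patients and a listing. Deaths get n (%). AESIs get SOC/PT tables; infusion reactions alone add events per administration and time to first reaction (SAP 5.8.2). Study duration varies: "It will range from months up to approximately 4 years, depending on conditions met in protocol Section 5.1". Results are shown for the Continue and New groups, and "data from both adolescent and adult patient subgroups will be summarized".

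**The concern.** A rate is meant to remove differences in follow-up. It does so only if the denominator holds time during which an event could have been recorded. For a patient who leaves at EOT, the stretch from day 28 to day 168 after the last dose cannot yield a recorded non-serious AE, yet it counts as time at risk if the patient is event-free. The error runs one way: the rate is too low. It is proportionally larger for shorter treatment, so groups with different time on drug, or different shares leaving at EOT, could show different rates at the same risk.

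The same excess arises for patients lost before 24 weeks of follow-up and for patients still on drug at an interim data cut. It also enters the optional Kaplan-Meier curves in SAP 5.8.1, which censor at the end of the TEAE period.

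Secondly, the outcomes that carry most weight in a long-term safety study have no rate. Crude percentages rise with follow-up, so the group followed for less time can look safer at the same risk.

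**Working it through.** The plan states no event rate, power or sample size calculation, so there is no figure to reproduce.

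**Inputs from the documents:** event-free credit to last dose + 168 days; EOT at last dose + 28 days; about 120 patients.

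**Assumed:** constant hazard h per year, the same in all groups and after the last dose; T years from first to last dose; share f of patients who leave at EOT.

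**1. Excess time per patient.** 168 − 28 = 140 days; 140 / 365 = 0.384 patient-years (the SAP converts with 365). Upper bound, if all 120 were event-free and left at EOT: 120 × 140 / 365 = 46.0 patient-years.

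**2. Planned rate if all leave at EOT (f = 1).** Observed time o = T + 28/365.25; credited time c = T + 168/365.25; p = 1 − exp(−h·o). Mean person-time = p/h + (1 − p)(c − o). Rate = p / person-time. At h = 0.10:

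| T (years) | p | person-time | rate | shortfall |
|---|---|---|---|---|
| 1 | 0.1021 | 1.0207 + 0.3442 = 1.3649 | 0.0748 | 25% |
| 2 | 0.1875 | 1.8752 + 0.3114 = 2.1866 | 0.0858 | 14% |
| 3 | 0.2648 | 2.6484 + 0.2818 = 2.9302 | 0.0904 | 10% |

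Ending time at the last visit removes the second term: 0.1021/1.0207 = 0.2648/2.6484 = 0.100.

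**3. Ratio between groups at equal risk.** f = 1: 0.0904/0.0748 = 1.21 for 3 vs 1 years; 0.0904/0.0858 = 1.05 for 3 vs 2 years. f = 0.5: rates 0.0874, 0.0929 and 0.0952, ratios 1.09 (3 vs 1) and 1.02 (3 vs 2). f = 0: all rates are 0.100. The 3 vs 1 ratio at f = 1 is also 1.21 at h = 0.02 and 0.50.

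**4. SAEs.** If SAEs are taken as observed for 30 days beyond EOT (day 58), the excess is 168 − 58 = 110 days. At h = 0.10 and f = 1, the rates for 1 and 3 years are 0.0803 and 0.0925, ratio 1.15.

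**5. Crude percentages at equal risk.** P = 1 − exp(−h(T + d/365.25)), with d = 168 if all complete follow-up and d = 28 if all stop at EOT. At h = 0.10 and d = 168: 13.6% (1 year), 21.8% (2 years) and 29.2% (3 years). Ratios as h goes from 0.02 to 0.50:

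| Contrast | d = 168 | d = 28 |
|---|---|---|
| 3 vs 1 years | 2.32 down to 1.59 | 2.80 down to 1.89 |
| 3 vs 2 years | 1.39 down to 1.16 | 1.47 down to 1.22 |

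For events that cluster early in treatment, these ratios are smaller.

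**The case against.** **SAEs and deaths are not simply unobserved after EOT.** A reader might infer that they are. Protocol 9.4.2 has the investigator, if informed, report SAEs with onset within 30 days of the end of study, or within 168 days of the last dose after early termination. Fatal and drug-related SAEs are reported later still. This stands and narrows the gap. But the reporting is passive, so follow-up is not complete, and it does not cover non-serious AEs.

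**Version lag.** The SAP is a first version, signed in October 2019, and it predates the waiver; both documents allow revision before database lock. So the mismatch should not be read as a choice made in knowledge of the waiver. The correction is still needed, because protocol 10.4.4.1 in the current version also keeps + 168 days without a cut.

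**Serious outcomes are not wholly without exposure information.** PT-level rates in the all-TEAE table include PTs that may be serious or belong to AESI groups. SAP 5.6.1 summarises patient-years of exposure. SAP 5.5 gives Kaplan-Meier displays for discontinuation, including for AEs. SAP 5.8.1 allows Kaplan-Meier curves for a serious-event signal. All true, but none gives a rate for any serious event, a grouped AESI, adjudicated CV events or deaths. The patient-years in SAP 4.6 run to last dose + 28 days and are not first-event time, and the serious-event curves are optional.

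**No inference is at stake.** This stands. The study is descriptive, safety comparisons are not tested, and the groups are not randomised.

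**Conclusion.** The person-time rule is wrong as written once the current protocol's waiver applies: it understates the planned all-TEAE rate whenever event-free patients leave at EOT. The text mismatch is certain; its size is not. At h = 0.10 with everyone leaving, the shortfall is 25% after 1 year on drug and 10% after 3 years. The between-group ratio reaches 1.21 for 3 vs 1 years but only 1.05 for 3 vs 2 years, and 1.09 for 3 vs 1 years if half leave. Hazard, durations and the share leaving are all assumptions, and follow-up by group is not given.

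The missing rates for serious TEAEs, AESI groups other than infusion reactions, adjudicated CV events and deaths are a secondary point: a cheap improvement against misreading. A reader might go further and conclude that the Continue versus New or adolescent versus adult results are invalid. The documents do not support that, since no such comparison is tested and unequal follow-up between these groups is possible but not shown.

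**What to change.** **(a) Person-time.** In SAP 5.8.1, for the all-TEAE rate and any Kaplan-Meier censoring, end person-time at the earliest of first event, last dose + 168 days, last study visit, death, or data cut-off for an interim analysis. Set the last-visit date in the same way for patients with and without events; a later safety report must not extend it, or time would be added only for patients with events. Count in the numerator only events up to that date.

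**(b) n (%).** Leave it unchanged under the existing TEAE definition. Footnote SAEs and deaths reported after the last visit but within last dose + 168 days as included in n (%) and outside the rate. Alternatively, state a separate SAE/death cut-off consistent with protocol 9.4.2 and apply it to numerator and denominator for all patients.

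**(c) Added rates.** Show the same first-event rate beside n (%) for serious TEAEs, event-based AESI groups other than infusion reactions and pregnancy, positively adjudicated CV events, and deaths in the TEAE period, by exposure group and adolescent status. For composite AESIs such as new-onset diabetes, use the date the criterion is first met and include only patients at risk.

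**Cost.** A small derivation change, an event-date rule for composites and a few columns; no new data and no testing. Rates in the roughly 14 adolescents will be imprecise and must be read with the counts.

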10.4.4.1. Adverse Events

Definitions

For safety variables, the following observation periods are defined:

- The pretreatment period is defined as the time from signing the ICF to before the first dose of study drug
- The open-label TEAE period is defined from the day of the first open-label study treatment administration to the day of the last open-label study treatment administration + 168 days
- The post-treatment period is defined as the time from the day after the end of the respective TEAE periods to the last study visit

Open-label TEAEs are defined as those events that developed, worsened, or became serious during the open-label TEAE period.

Analysis

All AEs reported in this study will be coded using the currently available version of the Medical Dictionary for Regulatory Activities (MedDRA®). Coding will be to lowest level terms. The verbatim text, the preferred term (PT), and the primary system organ class (SOC) will be listed.

Adverse event incidence tables will present data by SOC sorted alphabetically and PT sorted by decreasing frequency, and summarize the number (n) and percentage (%) of patients experiencing an AE. Multiple occurrences of the same event in the same patient will be counted only once in the tables. Data conventions for missing or partial AE dates will be addressed in the SAP. The denominator for computation of percentages is the respective SAF by the status of previous evinacumab treatment exposure, and again for the subpopulation of adolescent patients [yes/no].

Summaries of all TEAEs will at least include:

- All TEAEs (and patient listing)
- All treatment-emergent SAEs, including patient deaths (and patient listing)
- Treatment-emergent AESIs (eg, hypersensitivity and anaphylaxis, defined by a pre-specified grouping) (Section 9.4.3)
- TEAEs by severity (according to the grading scale outlined in Section 9.5.1), presented by SOC and PT, depicting the worse TEAE severity for those patients with multiple occurrences of the same event)
- All TEAEs leading to permanent treatment discontinuation (and patient listing)

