4.5. Patient Disposition

Patient disposition will include the description of patient status at major milestone decisions in the study, as well as the patient analysis populations.

For patient study status, patient milestone categories are defined below. As applicable, percentages will be calculated using a denominator of the number of patients treated with open-label study treatment, with two exceptions. Specifically, the two exceptions will be for the screened and screen failure categories, which will not have associated percentages shown.

- The total number of screened patients: defined as originally having met the inclusion criteria and signed the ICF
- The total number of patients failed screening
- The total number of patients enrolled, defined as all screened patients with a treatment kit number allocated and recorded in the IVRS database, regardless of whether the treatment kit was used.

- The total number of patients enrolled but not receiving study treatment.
- The total number of patients enrolled and receiving study treatment.
- The total numbers of patients who have participated in a previous evinacumab study (i.e., R1500-CL-1331 and R1500-CL-1629), or evinacumab-naïve patients with HoFH.
- The total number of patients who completed the OLTP as collected on the End of Treatment - Evinacumab e-CRF.
- The total number of patients who prematurely discontinued study treatment during the OLTP, and the reasons for discontinuation collected on the End of Treatment - Evinacumab e-CRF.
- The total number of patients ongoing in OLTP (applicable for the interim analyses)
- The total number of patients who complete the last study follow-up visit (i.e. Follow-up week 24).

The following patient populations for analyses are listed below:

- Safety (SAF) Analysis Set
- Efficacy Analysis Set (same as SAF)
- Pharmacokinetic (PK) Analysis Set
- Immunogenicity (ADA and NAb) Analysis Sets

The following patient listings will provide the details from the patient disposition table.

- A listing of patients treated but not enrolled, patients enrolled but not treated.
- A listing of patients prematurely discontinued from treatment, along with reasons for discontinuation.

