- All TEAEs by maximum severity (i.e., mild, moderate or severe)
- A common TEAE related to any clinically significant signal will be further characterized as appropriate. The characterization of the clinically significant signal can include Kaplan-Meier curves for time from first dose to first occurrence of selected TEAE, time to resolution, and event duration. Patients without any event will be censored at the end of the respective TEAE period.

Analysis of all treatment emergent serious adverse event(s)

- All Serious TEAEs by primary SOC, HLG, HLT, and PT
- All Serious TEAEs by primary SOC and PT
- Patient listings of serious TEAEs will be provided in the report appendix.
- All Serious TEAEs relationship (related/not related) to evinacumab
- A serious TEAE related to any clinically significant signal will be further characterized as appropriate. The characterization of the clinically significant signal can include Kaplan-Meier curves for time from first dose to first occurrence of selected TEAE, time to resolution, and event duration. Patients without any event will be censored at the end of the respective TEAE period.

Analysis of all treatment-emergent adverse event(s) leading to treatment discontinuation

- All TEAEs leading to permanent treatment discontinuation, by primary SOC, HLG, HLT, and PT
- All TEAEs leading to permanent treatment discontinuation, by primary SOC and PT

- Patient listings of TEAEs leading to permanent treatment discontinuation will be provided in the report appendix.
- A TEAE leading to permanent treatment discontinuation and related to any clinically significant signal will be further characterized as appropriate. The characterization of the clinically significant signal can include Kaplan-Meier curves for time from first dose to first occurrence of selected TEAE, time to resolution, and event duration. Patients without any event will be censored at the end of the respective TEAE period.

Post-treatment adverse events

- All post-treatment AEs by primary SOC and PT
- All post-treatment SAEs by primary SOC and PT

Analysis of Cardiovascular events

- TEAEs suspected of being CV events by primary SOC and PT
- TEAEs suspected of being CV events categorized by adjudicated outcome of positive, negative, or in-process (as applicable)

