6.3. Data Handling Convention for Missing Data

Missing data will not be imputed in listings. This section includes the methods for missing data imputation for some summary analyses, if necessary.

Date of First/Last Study Treatment

Since the study drug is administered at the site, the date of study drug administration is filled in e-CRF. No missing data is expected. Date of first/last administration is the first/last start date of study drug filled in e-CRF.

Adverse Event

If the intensity of a TEAE is missing, it will be classified as “severe” in the frequency tables by intensity of TEAEs. If the assessment of relationship of a TEAE to the investigational product is missing, it will be classified as related to the investigational product.

When the partial AE date information does not indicate that the AE started prior to study treatment or after the TEAE period, the AE will be classified as treatment-emergent.

Medication/Procedure

No imputation of medication/procedure start/end dates will be performed. If a medication date is missing or partially missing and it cannot be determined whether it was taken prior or

concomitantly or stopped prior to the first study treatment administration, it will be considered as concomitant medication/procedure.

Potentially Clinically Significant Value (PCSV)

If a patient has a missing baseline value, this patient will be grouped in the category “normal/missing at baseline.”

For PCSVs with 2 conditions, one based on a change from baseline value and the other on a threshold value or a normal range, with the first condition being missing, the PCSV will be based only on the second condition.

For a PCSV defined on a threshold and/or a normal range, this PCSV will be derived using this threshold if the normal range is missing; e.g., for eosinophils the PCSV is >0.5 giga/L or $>ULN$ if $ULN \geq 0.5$ giga/L. When ULN is missing, the value 0.5 should be used.

Measurements flagged as invalid by the laboratory will not be summarized or taken into account in the computation of PCSVs.

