7. TIMING OF STATISTICAL ANALYSES

In order to provide information from this study, data may be analyzed on an ongoing basis. The results will not be used to change the conduct of the ongoing study in any aspect.

Additionally, an interim analysis is planned for the subpopulation of adolescent patients. This planned interim analysis will be conducted as soon as all adolescent patients have been enrolled and all their data through week 24 has been collected and validated. For adolescent patients, the analysis will consist of the final analysis of the primary (safety) and secondary (lipids) endpoints collected during the initial 24 weeks of study treatment exposure. The safety and lipids analyses will be performed on all data collected and validated at the time of this adolescent subpopulation interim analysis.

If the study is terminated prematurely, only those parameters required for the development program and/or reporting to regulatory authorities will be summarized.

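### The TEAE rate per patient-year counts event-free patients to last dose + 168 days even when observation ended earlier, so the rate comes out too low

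*SAP*

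**What the plan says.** SAP 5.8.1 adds an event rate to the all-TEAE table by SOC and PT: patients with the event divided by total patient-years. A patient with the event contributes time to the first one. For the rest, "For a patient without an event, patient-year corresponds to the length of the TEAE period".

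Protocol 10.4.4.1 runs that period from the first open-label dose "to the day of the last open-label study treatment administration + 168 days", and SAP 4.8.1 does the same. Only the post-treatment period is bounded by the last study visit. The optional Kaplan-Meier curves in SAP 5.8.1 use the same end point: "Patients without any event will be censored at the end of the respective TEAE period".

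Five other provisions decide how much of that time is observed:

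- Protocol 9.4.6 collects AE information only to the last study visit.
- Protocol 5.1 lets patients moving to a CUP, EAP or ISS/IST skip the 24-week follow-up, so EOT is their last visit. Footnote 14 in protocol 8.1.3 places EOT 4 weeks after the last dose.
- SAP 4.5 expects some patients to be still in the open-label period at interim analyses.
- SAP 6.3 fixes the last dose for any data cut: "Date of first/last administration is the first/last start date of study drug filled in e-CRF".
- SAP 7 describes the adolescent interim in two ways, as endpoints "collected during the initial 24 weeks of study treatment exposure" and then: "The safety and lipids analyses will be performed on all data collected and validated at the time of this adolescent subpopulation interim analysis".

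**The concern.** Time in which no AE would routinely be recorded enters the denominator as event-free time, and almost nothing from it can enter the numerator. The rate can then only fall, which is the anti-conservative direction for a safety estimate. For a patient on treatment at an interim, part of the counted time lies after the cut-off and has not yet happened.

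The primary objectives are long-term safety, one of them in adolescents, and time in the study ranges from months to about 4 years. The per-patient-year rate is the figure in the all-TEAE table that allows for unequal time at risk. SAP 4.6 derives exposure in patient-years from last dose + 28 days, but the rate does not use it.

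**Working it through.** The plan states no event rate or patient-year total, so there is no figure to reproduce. The check asks how far the rate as written falls below the rate on observed time.

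**Inputs from the documents.** Counted time C ends at last dose + 168 days. For a patient who skips follow-up, observation O ends at last dose + 28 days for AEs, so 168 − 28 = 140 days are unobserved. Protocol 9.4.2 keeps SAEs reportable for a further 30 days, so O ends at last dose + 58 days for SAEs. For a patient on treatment at a cut-off, the latest 4-weekly dose was 0 to 28 days earlier, so C − O is 140 to 168 days. Two event frequencies come from the pivotal study described in protocol section 1, over 24 weeks on evinacumab: 66% with any AE and 11% with influenza-like illness.

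**Assumptions.** Constant hazard; even accrual over 24, 12 or 6 months; 48, 96 or 208 weeks from first to last dose; the share skipping follow-up. None of these is in the documents.

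**Formula.** With λ = −ln(1 − p)/168 per day, expected observed time to first event is PY = (1 − exp(−λO))/λ. Then reported/true = PY / (PY + exp(−λO)·(C − O)), with numerator and denominator each averaged over patients. For an uncommon event this tends to mean(O)/mean(C).

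**Adolescent interim, all available data.** The last adolescent enrolled has 168 days, so O = 168 + u days, with u uniform over the accrual period.

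| Accrual | Uncommon event | 11% per 24 weeks | 66% per 24 weeks |
|---|---|---|---|
| 24 months | 533.3/687.3 = 0.776 (22% low) | 0.802 (20%) | 0.929 (7%) |
| 12 months | 350.6/504.7 = 0.695 (31%) | 0.718 (28%) | 0.870 (13%) |
| 6 months | 259.3/413.8 = 0.627 (37%) | 0.647 (35%) | 0.801 (20%) |

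**Adolescent interim, data cut at week 24.** O = 168. C = 140 + 168 = 308 if the last counted dose is at week 20, or 168 + 168 = 336 if the patient is dosed on the cut day.

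- Uncommon event: 168/308 = 0.545 and 168/336 = 0.500, so 45–50% low.
- 11% event: 158.6/(158.6 + 124.6) = 0.560 and 158.6/(158.6 + 149.5) = 0.515, so 44–49% low.
- Any TEAE at 66%: 0.684 and 0.643, so 32–36% low.

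**Precision at the interim.** Fourteen adolescents over 6-month accrual give 14 × 259.3/365.25 = 9.9 patient-years. One event is 10.1 per 100 patient-years (exact 95% CI 0.25 to 56), and would be reported as 10.1 × 0.627 = 6.3.

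**Final analysis, uncommon event.** With T = 336, 672 or 1456 days from first to last dose, C = T + 168.

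| Share skipping | 48 weeks | 96 weeks | 208 weeks |
|---|---|---|---|
| All, AEs (O = T + 28) | 364/504 = 0.722 (28% low) | 700/840 = 0.833 (17%) | 1484/1624 = 0.914 (9%) |
| Half, AEs | 14% | 8% | 4% |
| Quarter, AEs | 7% | 4% | 2% |
| All, SAEs (O = T + 58) | 394/504 = 0.782 (22%) | 730/840 = 0.869 (13%) | 1514/1624 = 0.932 (7%) |
| Half, SAEs | 11% | 7% | 3% |
| Quarter, SAEs | 5% | 3% | 2% |
| None | 0% | 0% | 0% |

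For any TEAE at 66% per 24 weeks with all patients skipping, the shortfall is 9%, 1% and 0%.

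**Check of the remedy.** A simulation of 4,000,000 patients (SAE at 2% per 24 weeks, T = 336, all skipping) had a true rate of 4.39 per 100 patient-years. The rule as written gave 3.46. Capping time but still counting later-reported SAEs gave 4.76, about 8% high (394/364 = 1.082). Capping time and restricting the numerator gave 4.41, within simulation error.

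**The case against.** The definitions can be read as assuming observation throughout: both documents present these intervals as observation periods, and an uncapped period gives a patient whose last visit is EOT a post-treatment period of negative length. A programmer might truncate unprompted. But no truncation is written anywhere, and SAP 5.8.1 states a rule for event-free patients rather than leaving a gap.

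The follow-up waiver came after this SAP, a first version signed in October 2019, and both documents foresee revision before database lock. That is fair: the waiver part is an update still to be made. The interim part was there from the start.

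Protocol 9.4.2 also keeps SAEs reportable to 168 days after the last dose for early terminators, which closes the SAE gap for them. Waiver patients leave at study completion, so the 30-day window used above is the natural reading for them, followed by fatal or drug-related SAEs only. Protocol 8.1.4, on early termination, repeats the waiver, which leaves some doubt. The non-serious AE gap remains either way.

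The study is descriptive, the n (%) and severity tables stand, infusion reactions have their own per-administration rate, and the Kaplan-Meier curves are optional and affected only beyond true last contact. With about 14 adolescents, random error on one rare PT exceeds the bias. All of this stands and limits the consequence. The bias is nevertheless systematic across terms and always in the same direction.

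**Conclusion.** The concern holds. As written, the rate per patient-year is understated whenever an event-free patient's observation ends before last dose + 168 days. Patients who complete the 24-week follow-up are unaffected.

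The effect is largest for uncommon events at the adolescent interim: 22–37% under the accrual patterns assumed, or 45–50% if data are cut at week 24. At the final analysis it ranges from nil when nobody skips follow-up, through 2–7% when a quarter do, to 9–28% when all do. These are illustrations under constant hazard, not bounds. The missing cap and the direction of the bias are certain; the size depends on accrual, treatment duration and skip share, which the documents do not give. It should be fixed at the planned SAP revision.

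**What to change.** In SAP 5.8.1, for the per-patient-year rate and the Kaplan-Meier analyses, end time at risk at the earliest of:

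- last open-label dose + 168 days;
- the last study visit or contact at which AEs were assessed;
- death;
- the data cut-off date.

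Count in the numerator of these analyses only first events with onset inside that window. Leave the TEAE period as it is for classifying events and for the n (%) tables and listings, so that later-reported SAEs still appear there.

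The cost is SAP wording and one derived end-of-risk date applied to numerator and denominator; no visits are added. Reported rates will be slightly higher. A few late-reported SAEs, possibly fatal or drug-related, will count in n (%) but not in the rate, so the two can differ within a row. A table footnote should say so.
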